Autistic Spectrum Disorders (ASD) affect at least 1.1 % of the population (Baird, 2006; Christensen et al, 2016) and could be even twice this figure allowing for possible under-representation, and improving recognition in girls. Affected children, and adults, would be expected to have difficulties in social interaction and communication particularly with their peer group, and repetitive and sensory behaviours, often described as "social communication difficulties". These difficulties can vary from a child with no speech who has minimal interaction with his peers, to a child who may be desperate to make friends but lacks the understanding as to how to do so, whilst having the language to describe their interests in extensive detail. In the absence of a diagnostic test, a multidisciplinary assessment process is recommended in the UK. This requires information being gathered from various environments including home and educational settings, as well as observation and testing for evidence of autistic behaviours and/or patterns of thinking in clinic (NICE, 2011). Various tools have been developed to aid this process including formal structured history tools such as the Autism Diagnostic Interview (ADI-R) and the Diagnostic Interview for Social Communication Disorders (DISCO), and observational tools such as the Autism Diagnostic Observation Schedule (ADOS) and the NEuroPSYchological developmental assessment (NEPSY). However, as NICE recognised, "no single tool alone seems to have adequate sensitivity and specificity for diagnosis of autism" (NICE, 2013).

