Early use in 3 local Child Development Clinics suggested that the tool can help inform decision making around the need for further diagnostic assessment when used alongside parental history and information from other settings such as school questionnaires. In addition to information obtained from the questions within the tool, clinicians commented that they often obtained additional information around the child's interaction with themselves and with the tool. This experience, together with consultation with our wider team, including an academic expert in psychological testing, including Theory of Mind, ([name]), [name] (Head of OT, Royal Free), [name] (expert in use of digital technology in autism), and local parents, has allowed us to modify the story lines.

[figure not shown]

Figure 2. Affect recognition page

[figure not shown]
Figure 3. First Order Theory of Mind Test page adapted from Unexpected Contents False Belief Task.

Initial Pilot Study

(IRAS 217324 REC 16/LO/2138; HRA 201701014).

Pilot data, testing Pirates in 32 typically developing children (TD) attending a mainstream primary school (ages 4-11 years), and children attending the Child Development Centre following referral for possible ASD/social communication difficulties (ASD) showed a strong negative correlation (p<0.001) between number of errors and age (see figure 4), with most key stage one children (4-7.4 years) making 7 or fewer errors, and key stage two (7.5-11 years) less than 4. Taking data from children attending clinic for possible ASD in current study, suggests that most children where there were concerns about social communication were scoring at a higher level than this. Using the cut off scores identified in this study gave sensitivity 85%, specificity 92%, NPV 94%, PPV 79% which if confirmed in the proposed study would give a favourable performance in comparison with current screening tools such as the SCQ. By relating individual scores to these cut offs showed that typically developing children made a mean 1.9 (CI -2.5 to -1.3) fewer errors than the cut off, whilst children considered likely to have ASD clinically made a mean of 3.9 (CI 1.4 to 6.2) errors above the cut off, the difference being highly statistically significant (t test, p<0.00001). Children reported enjoying completing Pirates, whilst parents reported this increased their confidence in clinic assessment.

[figure not shown]

Figure 4. Total score compared to age in months

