Accuracy Parameters Protocol Version 2 29/9/17

a) Pilot study data only. b) includes data from early clinical use prior to pilot study

Aims and objectives

Test automated story with children in mainstream school, and with those already diagnosed with autistic spectrum disorder (ASD) in child development centres (CDCs).

- 1. Primary objective: Investigate parameters of screening tool in a group of 4 to 11 year old children, i.e. of primary school age, with known ASD; estimate discrimination from a group of children who are "typically developing", i.e. who do not have a clinical diagnosis of ASD.
- 2. Assess sensitivity/specificity of individual questions and relationship to age e.g. even typically developing younger children may not understand idiom.

Project design

Research methods

1. Sensitivity and Specificity of screening tool

User testing, two groups (children with a diagnosis of Autism Spectrum Disorder (ASD), typically developing children with no diagnosis (TD)) recruited to assess sensitivity of the automated story in a) a clinical environment (ASD, N=62), b) and in a school setting (TD, N=62).

Ethical approval

This has already been achieved for the initial pilot study in an investigation of typically developing children and children referred to a child development clinic for social communication difficulties (IRAS 217324 REC 16/LO/2138; HRA 201701014). We now hope to extend this to the proposed study through substantial amendment. The main change from the original pilot study is to change the "clinical group" from children referred for initial assessment of possible ASD to children already diagnosed with autism spectrum disorder. The methodology is essentially unchanged.

Subjects (including justification for sample size)

A sample of 124 children, suggested after consultation with Research Design service and Medical Statistician, with 62 typically developing children (31 male, 31 female), 62 with ASD (31 male, 31 female) aged 4 to 11 years will be recruited. With 62 children in each group, we will be able to further estimate the sensitivity and specificity of the software result with sufficient precision to enable us to isolate key parameters (Teare et al, 2014). For example, following Buderer (1996) with 62 ASD and 62 typical (i.e. a prevalence of ASD of 50%), assuming a sensitivity of 80%, the 95% confidence interval (CI) for sensitivity

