would be from 70 to 90%. The same applies for specificity. For this first stage, we aim to cluster children into two groups from the results of the application: "at risk/no risk" of ASD, which should match with ASD/No ASD. These two groups would then be further analysed against results to see if there is specific clustering around certain scores (total score, and for individual questions/sections), or responses, that may relate to other common associated impairments and co-morbid conditions which are: learning difficulty, language impairment, attention deficit hyperactivity disorder.

Recruitment

Children aged 4 to 11 years with ASD will be identified through CDCs in Sussex Community NHS Trust, by paediatric clinicians; typically developing children will be identified through the headteacher/appropriate member of staff in mainstream primary schools. The parents of children identified will be given a participant information sheet, and asked to contact the research team if they are interested in taking part. We estimate that we will need to approach 240 parents to achieve the full sample of 120 children. This is based on previous local recruitment rates for neuro-disability research of approximately 50% response. We will need to approach 12 potential recruits per month, with 6 recruited per month or 1.5 per week. This means the recruitment and data collection will be spread over 24 months, which we believe is feasible. We will aim to recruit and case match by age and gender.

Information leaflets will be given to the clinical group either in clinic by a member of the clinical care team or from the clinical team by post. Following this, parents will be contacted by the research team, and written informed consent will be sought. The pirate app testing will take place either in the home, clinic or school depending on adult preference.

Children in school will be given study information via school. Parents will then be contacted by the research team to discuss the study and if appropriate consent will be returned to school and then handed to research team. Phone contacts may be made to remaining parents to seek consent, where appropriate.

Inclusion criteria

Children aged 4 to 11 years, of primary school age:

- Group One: ASD: children with a recently confirmed diagnosis of ASD. Diagnosis will have involved full multidisciplinary diagnostic assessment by a CDC.
- Group Two: Typically developing group attending mainstream school

Exclusion criteria

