We will also calculate positive and negative predictive values. Sensitivity of the instrument with correct case finding will be based on clustering on types of ASD and typically developing children.

For this stage we aim to cluster children into two groups from the results: "at risk/not at risk" of ASD, which should match with ASD/Typically Developing.

These two groups would then go into secondary analysis to consider if there is clustering around certain scores or answers, and future study will explore relationship to other common associated impairments and co-morbid conditions such as: learning difficulty, language impairment, attention deficit hyperactivity disorder. We will estimate proportions of pass/fail recruited and retained for the clinical study and estimate sensitivity and specificity i.e. where sensitivity is the proportion of children with ASD that the tool correctly identifies, and specificity is the proportion without ASD that the screening tool correctly identifies. Thresholds and potential cut-off points for scores will be further clarified and defined using Receiver Operating Characteristic curves will to help refine the tool by comparing sensitivity/specificity and enable appropriate cut-offs to be decided. A logistic regression model will also be fitted to understand accuracy where the result of the tool is the predictor variable and we will also adjust for age and gender, as the at-risk of ASD and typically developing will be matched on these. If the tool detects accurately we will then aim to acquire European medical device regulation 93/42/EEC(MDD)8 for clinical trials [46]. If sensitivity/specificity trial is successful, the equipment will be used in a planned clinical trial.

Potential of research for patient care

Improving information at initial screening will reduce stress and anxiety for children and families and improve the experience and engagement of children. Further, quicker and better decision making will aid in determining which children require full assessment.

References

Autism Achieve Alliance (2014) Autism Spectrum Disorders: Waiting for assessment. Executive Summary, 6 August 2014 (accessed 26/2/2016)

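### PPV and NPV are planned in a sample recruited at 50% ASD, so values read from that table reflect the quota, are not valid for Stage One clinics, and cannot be compared with the pilot's 79% and 94%

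*Protocol*

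**What the plan says.** Under Data analysis, Quantitative Analysis, the protocol commits to sensitivity and specificity and adds "We will also calculate positive and negative predictive values". It gives no target prevalence, no re-weighting and no caveat.

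Under Subjects, the sample is planned "with 62 ASD and 62 typical (i.e. a prevalence of ASD of 50" per cent. The Recruitment and Inclusion criteria sections draw the cases from children already diagnosed at child development centres (CDCs), and the controls separately from mainstream schools. The Exclusion criteria keep children out of the control results if they have been referred to a child development team before or have certain known difficulties.

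Under Initial Pilot Study, the protocol reports that the existing cut-offs "gave sensitivity 85%, specificity 92%, NPV 94%, PPV 79% which if confirmed in the proposed study would give a favourable performance" relative to current screening tools. The Ethical approval section says that the clinical group has changed since the pilot, from children referred for assessment to children with a diagnosis.

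**The concern.** Sensitivity and specificity are each calculated within one group, so the ratio of the groups does not affect them. PPV and NPV combine the two groups, so they move with the share that has ASD. Here that share is a recruitment quota and tells us nothing about any setting where the tool would be used.

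Two things are at stake. First, the tool is meant to inform the Stage One decision on whether to proceed to full assessment, and predictive values are the figures a clinician there would naturally read. Second, the pilot section groups PPV and NPV with sensitivity and specificity as figures this study might confirm. The pilot had a different mix, so a reader comparing the two studies would see changes produced by the sampling alone.

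**Working it through.** **Inputs.** Group sizes of 62 and 62, and the planning value of 80%, come from Subjects. Pilot sensitivity (Se) 85%, specificity (Sp) 92%, PPV 79% and NPV 94% come from Initial Pilot Study. The protocol gives no ASD prevalence among Stage One referrals, so 20% to 80% is used as an assumption.

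**1. The plan's own precision figure.** For "the 95% confidence interval (CI) for sensitivity" the protocol says it "would be from 70 to 90%. The same applies for specificity". The simple (Wald) interval is 0.80 ± 1.96 × √(0.80 × 0.20 / 62) = 0.80 ± 0.0996, or 70.0% to 90.0%. This reproduces. The group size also reproduces: 1.96² × 0.16 / 0.10² = 61.5, rounded up to 62. The sample size is therefore built on sensitivity and specificity, and predictive values play no part in it.

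**2. The mix implied by the pilot.** With q for the share with ASD:

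- PPV = Se·q / [Se·q + (1 − Sp)(1 − q)]
- NPV = Sp(1 − q) / [Sp(1 − q) + (1 − Se)q]

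Solving each for q:

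- From PPV: q/(1 − q) = (0.79/0.21) × (0.08/0.85) = 0.354, so q = 26.1%.
- From NPV: (1 − q)/q = (0.94/0.06) × (0.15/0.92) = 2.554, so q = 28.1%.

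Allowing for rounding in the reported figures, the ranges are 24.3% to 28.1% and 25.6% to 30.7%, which overlap at about 26% to 28%. The smallest tables that fit all four rounded figures have 13 children with ASD and 36 or 37 without. For 13 and 36: 11/13 = 85%, 33/36 = 92%, 11/14 = 79%, 33/35 = 94%. These tables are arithmetic reconstructions; the protocol does not report the pilot counts.

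**3. The same tool in the 62:62 sample.** With Se 85%, Sp 92% and q = 0.50:

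- PPV = 0.425 / (0.425 + 0.040) = 91.4%, about 12 points above 79%.
- NPV = 0.460 / (0.460 + 0.075) = 86.0%, 8 points below 94%.

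**4. What it would take to match the pilot's PPV and NPV here.** At q = 0.50, PPV 79% needs Se/(1 − Sp) = 0.79/0.21 = 3.762, and NPV 94% needs Sp/(1 − Se) = 0.94/0.06 = 15.667. Solving together gives Se = 95.2% and Sp = 74.7%. Matching the predictive values would therefore mean missing the pilot's sensitivity and specificity. The four figures cannot all be confirmed in this design.

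**5. Sensitivity to prevalence, at Se 85% and Sp 92%.**

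| Share with ASD | PPV | NPV |
|---|---|---|
| 20% (assumed) | 0.170/0.234 = 72.6% | 0.736/0.766 = 96.1% |
| 27% (pilot's implied mix) | 0.2295/0.2879 = 79.7% | 0.6716/0.7121 = 94.3% |
| 50% (this sample) | 91.4% | 86.0% |
| 60% (assumed) | 0.510/0.542 = 94.1% | 0.368/0.458 = 80.3% |
| 80% (assumed) | 0.680/0.696 = 97.7% | 0.184/0.304 = 60.5% |

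The likelihood ratios do not depend on the share: 0.85/0.08 = 10.6 for a positive result and 0.15/0.92 = 0.16 for a negative one.

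**The case against.** The strongest reply is that predictive values take up one sentence. The primary objective, the sample size, the ROC work and the condition for moving to a clinical trial all rest on accuracy and discrimination, mainly sensitivity and specificity. This stands, and it limits the weight of the point.

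A second reply is that the protocol does not say the values will be read unadjusted from the table, and a statistical analysis plan could name a prevalence. That is possible. But the protocol commits to the calculation without condition, in a sample it describes itself as 50% ASD, and presents the pilot's PPV and NPV as figures that might be confirmed. Both sentences need correcting whatever a later plan says.

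Some stronger readings are tempting, but the documents do not support them:

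- A reader might infer that a 50% mix matches no clinic, or that PPV is bound to be overstated. The Stage One prevalence is not given. It could be near 50%, and above 50% the study's PPV would be too low.
- A reader might take the protocol's statement that ASD "affect at least 1.1 % of the population" and quote a PPV of about 11% (0.00935/0.08847). But the tool is meant for children at initial clinical contact, not for population screening.
- A reader might infer that the results would look better than the pilot's. Only PPV would; NPV would look worse.
- A reader might take the pilot section as asserting that this study will confirm PPV and NPV. The wording is conditional, so narrowing it is enough.

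**Conclusion.** The point holds as a should-fix. PPV and NPV taken from the 62:62 table would describe the recruitment quota. They are not valid estimates for Stage One clinics and cannot be compared with the pilot's. With the tool's accuracy unchanged, they would read 91% and 86% against 79% and 94%.

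The comparison assumes that the pilot's four figures come from a single table and that sensitivity and specificity are reproduced exactly. The implied 26% to 28% is derived, not reported. The pilot's own predictive values also depend on its sampling mix, so they are no clinic benchmark either.

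Even if a clinic happened to have 50% ASD, its children without ASD would be referred children, and the control results leave out children with a prior referral. Adjusting for prevalence corrects the mix but not this difference in the kind of child tested. Sensitivity and specificity are untouched by the quota, although the contrast of diagnosed cases with typically developing controls bears on them too.

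**What to change.** Replace the sentence in Quantitative Analysis with text to this effect:

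> Predictive values will not be calculated from the 62:62 table. PPV and NPV will be derived by Bayes' theorem from the estimated sensitivity and specificity, with 95% confidence intervals, over a stated range of ASD prevalence among Stage One referrals. Positive and negative likelihood ratios will be reported from the study. The derived values rest on diagnosed cases and typically developing controls, and the control results omit previously referred children and those with the listed known difficulties. They may therefore not carry over to children seen at Stage One.

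The range has to be chosen, because the documents give none. It could be an assumed 20% to 80%, which at 85% and 92% gives PPV 73% to 98% and NPV 96% to 61%. The proportion diagnosed in the CDCs' own records would be better, if available. At a fixed prevalence, the odds of ASD after a test result are the prior odds times the likelihood ratio, so the intervals follow directly from those of the likelihood ratios.

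In Initial Pilot Study, limit the conditional remark about confirmation to sensitivity and specificity.

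The cost is a short rewording and one small table. No further children need to be tested, but using CDC records would mean extracting a figure the protocol does not contain. Predictive values would appear as a range, which may be more or less favourable than the 50% figures.

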- Child non-verbal or severe learning difficulties or English as second language;
- Typically developing children with prior referral to a child development team or with known social communication or language difficulties or ADHD. These children may take part but results will not be included in typically developing results for analysis.
- Child not of primary school age (i.e. 4 to 11 years).

Process of gaining consent

All necessary consents will be obtained from parents and children following research ethical approval in advance of recruitment and data collection. Individual school policy will be followed for consenting and acceptability of school recruitment. A member of the team experienced in education will lead school recruitment (ex-Assistant Head teacher). Parental consent and child assent will be sought. Two schools in the local area have indicated interest in the study giving a potential recruitment base of 800 children.

Test

Participants in both groups will be given the screening tool to complete. A medical researcher will administer the application to children with ASD and typically developing children in clinic and/or in schools or in the child's home. The story produces pass/fail results recorded anonymously within the software. This data will be transferred to a paper record, and automatically deletes from the software once the individual testing is completed. Current cut-offs are set at 7 errors for key stage one children (4-7.4 YO) and 4 errors for key stage two (7.5-11YO). Results will be collated to attempt to see if it is possible for scores to cluster clearly around typical and ASD populations. There is already evidence of clustering for a clinically abnormal versus typically developing population.

Data analysis

Quantitative Analysis

The main aspects of data recorded will analyse the ASD group: SCQ score, clinical notes confirmation of ASD (yes/no), and automated story result (at risk of ASD yes/no using cut-off scores). Typically developing group will be scored only on automated story result (given that there has been no clinical contact). These will be used to assess sensitivity and specificity with three levels of cross sectional analysis:

- a) Clinical notes diagnosis (i.e. does school observation support diagnosis Yes/No) vs. automated story result
- b) SCQ score vs. automated story result
- c) SCQ score + clinical notes (i.e. does school observation support diagnosis Yes/No) vs. automated story result

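### The secondary clustering step compares scores and answers between groups that the tool defines from those same answers; it should compare the diagnostic groups

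*Protocol*

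**What the plan says.** The step appears twice in the Protocol, and both times the sentence before it names groups formed by the tool.

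- *Subjects (including justification for sample size)*: "we aim to cluster children into two groups from the results of the application: 'at risk/no risk' of ASD". The groups are then examined for "specific clustering around certain scores (total score, and for individual questions/sections), or responses", with a link to co-morbid conditions.
- *Data analysis, Quantitative Analysis*: "For this stage we aim to cluster children into two groups from the results: 'at risk/not at risk' of ASD", followed by "These two groups would then go into secondary analysis to consider if there is clustering around certain scores or answers". Here the link to co-morbid conditions is deferred to a future study.

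The rule behind the label is in *Test*: "Current cut-offs are set at 7 errors for key stage one children (4-7.4 YO) and 4 errors for key stage two (7.5-11YO". The Quantitative Analysis section confirms that the tool's yes/no result comes from these cut-offs. In both places the protocol says only that the tool's groups should match the diagnostic groups. It does not substitute one for the other.

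Objective 2, under *Aims and objectives*, is stated separately: "Assess sensitivity/specificity of individual questions and relationship to age".

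**The concern.** At-risk status is a threshold on total errors, and total errors are the sum of the failed questions. Asking whether scores or answers cluster in the at-risk group therefore partly asks whether a sum is related to its own parts. The answer is yes whether or not the parts relate to ASD.

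The risk is one of interpretation. A memory, naming or language control question, if it counts as an error, could appear to go with being at risk of ASD only because failing it helps to put the child in that group. A reader could take this as evidence that the question discriminates ASD. Diagnosis is known for every child by design, so a comparison free of this problem is available from the same data.

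**Working it through.** **Inputs.** From the Protocol: 62 children with ASD and 62 typically developing; cut-offs of 7 errors (key stage one) and 4 (key stage two). Assumed: half of each group in each key stage; 28 scoring questions, which is the number of pass/fail rows that can be counted on the score sheet (the protocol does not say whether control questions count as errors); independent errors within a child; the mean error counts below; Fisher's exact test at two-sided 5%. At risk was taken both as at-or-above and as above the cut-off.

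**1. The plan's own figure.** The protocol gives no figure for this step. Its precision statement reproduces: 0.80 ± 1.96 × √(0.80 × 0.20 / 62) = 0.80 ± 0.10, or 70 to 90%. At that assumed sensitivity, with the same for specificity, 0.20 × 62 ≈ 12 children in each diagnostic group fall on the wrong side. The tool's groups and the diagnostic groups would then differ for about 25 of 124 children.

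**2. Total score.** Within a key stage every at-risk child lies on one side of the cut-off and every other child on the other. Separation is certain.

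**3. A single unrelated question.** Let X = 1 for an error on the question, with probability p in both diagnostic groups. Let R be the errors on the other 27 questions, and let a child be at risk if X + R ≥ c. A child who fails the question is at risk if R ≥ c − 1; a child who passes it needs R ≥ c. The gap is Q = P(R = c − 1), which is above zero. With A the proportion at risk, the difference in error rate on that question between the tool's groups is

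D = p(1 − p) × Q / [A(1 − A)].

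Between diagnostic groups it is 0.

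- *Tool near pilot accuracy.* Mean errors on the other 27 questions (key stage one, two) are 4 and 1.7 in typically developing children, 9 and 5.7 in ASD. With binomial R, P(R = 6) is 0.108 and 0.081, and P(R = 3) is 0.153 and 0.093, so the mean Q is 0.109. With p = 0.30 and A = 0.502, D = 0.21 × 0.109 / 0.250 = 0.092, or 9 points.
- *Uninformative tool.* Means are 6 and 3.2 in both groups. Q is the mean of 0.182 and 0.236, which is 0.209. With p = 0.50 and A = 0.501, D = 0.25 × 0.209 / 0.250 = 0.209, or 21 points.

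Simulation (2,000 studies per setting) gives 9.3 and 20.8 points for these two cases, in agreement.

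**4. How often the question is flagged.** Ranges cover both cut-off rules and the error rates tried for the unrelated question.

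| Assumed tool | Sensitivity / specificity | Difference, tool's groups | Flagged, tool's groups | Flagged, diagnosis |
|---|---|---|---|---|
| Near pilot | 0.86–0.89 / 0.81–0.88 | +7 to +11 points | 13–21% | 3–4% |
| Moderate | 0.71 / 0.70–0.73 | +14 points | 35–38% | 3–4% |
| Uninformative | 0.43–0.50 / 0.50–0.57 | +12 to +21 points | 32–61% | 3–4% |

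**5. No question related to ASD.** In 1,000 simulated studies per cut-off, 34% (cut-off 7) and 33% (cut-off 4) of the 28 questions were flagged between the tool's groups, against 2.8% and 2.3% by diagnosis. Mean total score differed by 3.6 and 2.9 errors. At least one question was flagged in every study.

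**6. Sensitivity to the assumptions.** A different set-up, with 14 informative and 14 unrelated questions (sensitivity 0.78–0.81, specificity 0.80–0.91), flagged 9 to 46% of the unrelated questions by tool group, against about 2% by diagnosis. The direction is stable; the size is not.

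**The case against.** **The groups may be meant as ASD and typically developing.** The protocol uses its labels loosely. Where it describes the logistic regression, it calls the group matched on age and gender at-risk, and that can only be the recruited ASD group. This makes a slip of wording plausible. However, in both places the sentence directly before the step names the groups formed from the tool's results. If diagnosis was meant, the text needs the same edit.

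**The step may be about co-morbidity.** The Subjects section does tie the patterns to learning difficulty, language impairment and ADHD. Quantitative Analysis leaves that link to future work and keeps the comparison of scores and answers, so the circularity remains.

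Some stronger readings are tempting, and the document does not support them:

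- *That objective 2 cannot be answered.* Sensitivity and specificity are defined in Quantitative Analysis against children with and without ASD, so the objective already requires diagnosis as reference. The *Test* section also plans to look at scores by typical and ASD population.
- *That refinement of the tool will be misdirected.* The stated route for refinement is the ROC curve. Nowhere is a question kept or dropped on the clustering step.
- *That every unrelated question will appear to cluster.* Certainty applies to total score within a key stage. For a single question there is bias and an inflated false-positive rate; near pilot accuracy most unrelated questions would still not be flagged.
- *That the lack of multiplicity control is an error.* The protocol sets no test or significance level for this step, and such detail commonly sits in a SAP.

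**Conclusion.** The concern holds for the secondary clustering step and for nothing wider. As written, the step compares the tool's answers between groups made from those answers. It can show that the tool is internally consistent; it cannot show that a score or question relates to ASD.

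The separation of total score follows from the cut-off rule alone. For a single question, the positive expected difference needs only that the question counts towards the total and that its errors are independent of the others. The flagging rates of roughly 10 to 20% near pilot accuracy and 30 to 60% for an uninformative tool, against 2 to 4% by diagnosis, rest on assumed error rates, 28 scoring questions and a 5% test that the protocol does not specify. They indicate scale and are not predictions. The sample size is not affected.

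**What to change.** In both places (*Subjects* and *Quantitative Analysis*), state that scores, sections and individual questions are compared between the diagnostic groups, ASD and typically developing. Report the results by key stage with 95% confidence intervals.

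If a comparison by tool result is still wanted, either compute at-risk status from the score with the question under study removed, or describe the result as internal consistency and not as evidence of discrimination of ASD.

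The cost is a change of wording in two paragraphs. The data are already to be collected, and recruitment and sample size do not change. The small downside is that fewer questions will look discriminating.
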